## **7.3 Common Adverse Events**

### **7.3.1 CA hemorrhage**

Best care criteria defined by the American Heart Association (AHA) guidelines for management of ICH will be the standards of care for all general medical care in this protocol. Specifically, the guidelines are (i) Stroke Council special writing group

guidelines for the management of ICH (74), (ii) European Stroke Initiative (EUSI) Guidelines for the management of intracranial hemorrhage (104), and (iii) the AANS guidelines for management of elevated intracranial pressure (105). Management may include blood pressure reduction, use of platelets and prothrombotic agents, and use of a surgical procedure. The care team is required to preserve life and functional outcomes in these instances. The management of each adverse event will be recorded and will be reviewed by the safety monitoring team.

If a CA symptomatic bleed is verified as per adjudicated criteria (20), including a rebleed of prior lesion or new bleed from another lesion, then a safety endpoint will have been reached, and the subject will be notified, and decision is made to cease the study intervention. Patients will remain in the study for the remaining scheduled follow-ups. The lesion that has hemorrhaged shall be considered for treatment as per current guidelines and standards of care.

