## 8. CRITERIA FOR INTERVENTION DISCONTINUATION

Atorvastatin/Placebo administration will be discontinued for any of the following reasons (designated as serious AEs or Category C in the preceding Table 2):

- Symptomatic intracerebral hemorrhage (ICH) whether primary, arising from index cavernous malformation that previously bled, or in other lesion, or other ICH of any kind
- Severe allergic reaction
- Rhabdomyolysis
- Markedly elevated liver enzymes
- Liver failure
- Pancreatitis
- Pregnancy
- Intolerable adverse events that persist or recur after serial dose reduction.
- In the investigator's judgment, withdrawal from the trial would be in the subject's best interest (Drug interaction/glycemic control).
- The subject or legal representative withdraws consent, or patient undergoes surgical resection or irradiation of CCM lesion, other brain surgery or irradiation for any cause.
- Patient develops clinical indications for statin use for cholesterol or cardiovascular indications unrelated to CCM.

If one or more of these events occur after commencing the study drug, the subject will be considered to have reached a safety endpoint. Study drug or placebo shall be discontinued. All subjects reaching safety endpoints will be followed through the 24-month follow up visit as a part of the outcome assessment for the study. An attempt will be made to contact subjects who withdraw from the study or who are lost to follow up for safety evaluation. If these subjects wish not to cooperate there will be no additional follow up.

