## 9.3 Sample Size and Accrual

### 9.3.1 Sample size and Treatment Effect Estimation

Sample size calculations were based on providing sufficient power to test the primary hypothesis, that the proposed intervention impacts QSM biomarker activity (indicative of reduced or increased lesional bleeding) during 2 years of prospective follow-up after a recent CA SH. **The primary outcome is the mean % change in lesional QSM per year (called the change score).** Each patient contributes two outcome measurements (at year 1 and year 2, i.e. epochs). Evaluation of the intervention on this outcome will be performed as a time-averaged difference between two arms using a repeated measures analysis implemented as a linear mixed model and intention-to-treat principle (110).

**Estimating a “First-in-Man” treatment effect on a biomarker** can be difficult when such effect is demonstrated mechanistically but the translation to a human effect size remains unknown (111). Based on pilot data linking QSM change to clinical events, **we propose a minimum, clinically meaningful and mechanistically plausible treatment effect to be a 20% absolute difference in the mean change score.** It would be “a minimum expected effect”, <1/2 the mean 44% QSM increase observed with CA bleed or growth during longitudinal 1-year follow-up of previously stable lesions; and “clinically meaningful”, > 3X the threshold of QSM change associated with maximum sensitivity-specificity on ROC analyses (58). The absolute QSM effect size postulated herein is “plausible mechanistically”. It would be 0.0068 ppm [20% of 0.0340 ppm mean QSM change observed during follow-up of CA with SH (59)], 6-22 folds lower than the observed range of atorvastatin treatment effect on Perls stain intensity in *Ccm1* and *Ccm3* murine models (Figures 2, 3, 5).

One-year %QSM change in 16 pilot study patients (Figure 7), followed for either 1 or 2 years (22 patient-year epochs), was used to estimate the 1-year/patient standard deviation and within-patient correlation of the primary outcome in trial candidates. A sample size calculation was performed using a repeated measures analysis of two annual percent QSM change scores, assuming a two-tailed test, power = 0.9 and alpha = 0.05 (112). The actual within person correction from the pilot data was estimated at approximately -0.6 (Spearman); however, as this was based on only 6 patients with two-year’s

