worth of data, we chose the more conservative within person correlation of 0 for our sample size estimates. In addition, we assumed a common standard deviation of 30 for the mean percent change score, which to be conservative is about 20% larger than the standard deviation in our pilot data. **To detect a 20% absolute difference between the mean change score in each arm, based on two annual change scores measured per patient (at years 1 and 2), 25 patients per arm would be required.** To detect a smaller or larger effect size, an absolute difference of 15% or 25%, 44 or 17 patients per arm would be required, respectively (Hintze 2014, PASS v13, NCSS, Kaysville, Utah, USA [www.ncss.com](http://www.ncss.com)). The sample size was further expanded by 37.5% to accommodate the highest estimate of missing data from all causes as discussed below. Hence we shall aim to enroll **40 patients/arm, 80 total subjects.**

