### **9.3.2 Potential Missing Data, Attrition and Premature Trial Endpoint**

We considered all potential causes of missing data and we developed strategies to minimize and mitigate them. In initial pilot studies, 34 of 177 (19%) QSM assessments in CA patients were unusable due to technical reasons (mostly patient movement during image acquisition). We eliminated this problem in the most recent 25 consecutive cases with specific patient instructions. We now implement a further step of reviewing the QSM acquisition, and rapidly processing it (10 minutes on local Matlab computer terminals in our laboratory). This allows us to repeat the QSM acquisition if needed, before proceeding with contrast injection for DCEQP measurements. This “chaperoned biomarker acquisition” reduces to virtually zero the rate of missing QSM measures (See letter by [name] and Protocol Section 6.5). We nevertheless project up to 10% missing biomarker data related to imaging (claustrophobia, etc.). We further project an additional 10% missing data due to imperfect follow-up, higher than that recorded in recent trials conducted by our teams (113, 114).

Up to 20% of subjects randomized to atorvastatin (10% of trial subjects) might not tolerate the 80 mg/day dose. Many will continue the drug at the lower dose. In fact, **serious side effects or intolerance of the lower dose are expected to result in attrition in less than 5% of cases**, per extensive meta-analyses of trial experience with the study drug (See Protection of Human Subjects; and Protocol section 7.3). Another **20-30% of cases might reach a prespecified study endpoint** because of SH, and they would also stop the drug before the end of the 2-years follow-up. All subjects who stop the drug, and those with non-compliance as defined, will still be followed for the full 2 years with scheduled clinical and imaging assessments, and will be included in the **primary analysis per intention-to-treat**.

To permit secondary analysis per treatment rendered, at the power and Type I error described above, we decided to **expand the sample size by an ample 37.5%, factoring the highest combined estimates of missing data and attrition.**

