### **9.5 Data analysis**

Exploratory analyses for quality assurance and understanding of missing data patterns and distributions will be performed on the outcomes and all measurements to be used in the primary and secondary analyses. For the **primary aim**, a linear mixed model will be used that adjusts for gender to evaluate the difference between the two arms in the QSM change of the index hemorrhagic lesion per patient. Adjustment for gender is necessary because the patients will be randomized by gender stratification. Not control-

ling for stratification variables can lead to upwardly biased standard errors and a decreased power (116). The model accounts for within-patient correlation between the measurements (117, 118). Patients with outcome measurements in both periods will be included in the initial intention-to-treat analysis. A secondary analysis of the percent QSM change per year shall be conducted per treatment rendered for all patients with at least one annual epoch of measurements. Significance levels are assumed as per sample size calculations.

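### QSM after resection or irradiation of the index lesion has no scoring rule, so surgery is either read as drug response or removes the subject from the primary analysis

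*Combined protocol and SAP*

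**What the plan says.** - **Drug stops, follow-up continues.** Section 8 lists among its discontinuation reasons that the "patient undergoes surgical resection or irradiation of CCM lesion, other brain surgery or irradiation for any cause". It treats this as a safety endpoint and follows the subject to the 24-month visit for outcome assessment.
- **The subject stays in the primary analysis.** Section 9.3.2 states that subjects who stop drug "will still be followed for the full 2 years with scheduled clinical and imaging assessments, and will be included in the" primary intention-to-treat analysis.
- **Lesion treatment during the trial is foreseen.** On a verified symptomatic bleed, Section 7.3.1 says: "The lesion that has hemorrhaged shall be considered for treatment as per current guidelines and standards of care". Section 6.4.2 plans assays on lesions excised during the study. Section 2.1 describes excision as usually considered after recurrent symptomatic hemorrhage.
- **The analysis set is narrower.** Section 9.5 (likewise 9.2) says: "Patients with outcome measurements in both periods will be included in the initial intention-to-treat analysis".
- **The measurement.** Section 6.5.3 defines lesional QSM as the mean over regions drawn around the index lesion on each slice where it can be seen.
- **Missing data.** Section 9.5 offers multiple imputation under missing-at-random using baseline demographics, a tipping-point analysis and a worst-case imputation for the active arm. These are sensitivity analyses, and none mentions surgery or irradiation.

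**The concern.** Once the index lesion has been resected, its QSM no longer measures drug effect on lesional bleeding. The plan keeps these subjects in the imaging outcome without saying what value they contribute, and its two inclusion rules point in opposite directions.

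If a post-resection scan is scored, a change produced by surgery enters as drug response. If it is left unscored, the both-periods rule removes the subject together with any valid year-1 epoch, which contradicts Section 9.3.2.

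Resection is not a random event here. The protocol's own background places it after a rebleed, so the affected subjects are likely to be those with large QSM increases. If atorvastatin had more of them, a signal of harm would be weakened. If placebo had more, a benefit would be diluted. The secondary QSM biomarker-event analysis is exposed too, since a scored post-resection fall would read as a non-event.

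Without a rule, the choice would be made after the fact, on the subjects most informative about bleeding.

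**Working it through.** **1. The plan's own sample size.** Section 9.3.1 gives the inputs: "assuming a two-tailed test, power = 0.9 and alpha = 0.05"; "To detect a 20% absolute difference between the mean change score in each arm"; "we assumed a common standard deviation of 30 for the mean percent change score"; "we chose the more conservative within person correlation of 0 for our sample size estimates".

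- SD of a patient's two-epoch mean = 30 × √((1+0)/2) = 21.21.
- n per arm = 2 × (1.960+1.282)² × 21.21² / 20² = 23.6, so 24 by the normal approximation. The noncentral t gives 25, as stated.
- 25/(1−0.375) = 40 per arm, as stated.

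The sample size is not in dispute. Power at 40 per arm is 0.988, so losing a few subjects matters for bias more than for power.

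**2. Possible number of resections.** Section 9.3.2 expects 20–30% of subjects to reach the hemorrhage endpoint: 80 × 0.20 = 16 to 80 × 0.30 = 24. Section 3.1 reports that 7 of 37 clinic patients with a recent hemorrhage had the lesion excised. Applying that share (assumption): 16 × 7/37 = 3.0 and 24 × 7/37 = 4.5.

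**3. Illustrative model.** Section 2.2 gives +44% for epochs with bleeding or growth and −3.2% for stable ones, both from previously stable lesions. As a check, mixing them at 5 bleed epochs in 22 gives 5/22 × 44 + 17/22 × (−3.2) = +7.5%, close to the +7.93% in the pilot cohort with recent hemorrhage.

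A rebleeder has one epoch of each kind, so averages (44−3.2)/2 = 20.4, which is 23.6 above a stable subject. Let q be an arm's 2-year rebleed proportion and s the share of rebleeders resected, with s = 0.2 (close to 7/37). The rebleed rates below are assumptions.

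- Difference without resection: 23.6 × (q_A − q_P).
- Resected subjects dropped: arm mean = −3.2 + 23.6 × q(1−s)/(1−qs).
- Resected subjects scored v in the bleed epoch: difference = (q_A − q_P) × (23.6 − s(44−v)/2).

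| Rebleeds, atorvastatin vs placebo | No resection | Dropped | Scored −50% | Scored −100% |
|---|---|---|---|---|
| 40% vs 20% | +4.72 | +4.28 | +2.84 | +1.84 |
| 15% vs 30% | −3.54 | −3.11 | −2.13 | −1.38 |

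Dropping shrinks the difference by 0.44/4.72 = 9% and 0.43/3.54 = 12%, with no sign change. Scoring moves it by 1.4 to 2.9 points. Scoring reverses the sign only if s exceeds 23.6/47 = 0.50 (v = −50) or 23.6/72 = 0.33 (v = −100).

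**4. Per subject.** One resected subject scored −50% or −100% instead of +44% moves that arm's mean by −94/(2n) or −144/(2n). This is −1.9 or −2.9 points at n = 25, and −1.2 or −1.8 at n = 40.

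**5. Balanced arms.** With equal rebleed and surgery rates the bias is zero. By simulation, −100% scores in 5% of patients raise the SD of the patient mean from 21.2 to 23.6 and lower power at 25 per arm from 0.92 to 0.85 (normal approximation).

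**6. Does keeping pre-procedure epochs suffice?** Take 40% vs 20%, pooling the available epochs at correlation 0.

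- Bleed and resection both in year 2, year-1 epoch retained: 47.2 × [0.32/1.92 − 0.16/1.96] = 4.01.
- Bleed captured at month 12, resection afterwards: 47.2 × [0.40/1.92 − 0.20/1.96] = 5.02.

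The no-resection value of 4.72 lies between them. Retention helps when the bleed has already been scanned. It does not recover a bleed that was never scanned.

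**The case against.** **Lost iron.** A reader might infer that the plan credits a resected subject with lost iron. The documents do not support that. QSM is a regional mean, not total iron, and a fully excised lesion may leave no region to draw, so a missing value is at least as natural. The −50% and −100% scores have no source in the protocol. If the resection falls in year 1, the year-2 epoch would also start from a post-resection base.

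**Hidden harm.** A reader might also infer that operated rebleeds vanish from the trial. They do not. Symptomatic hemorrhage is a separate secondary outcome with its own model, rebleeding goes to the safety monitor by arm, and Section 9.4.2 sets a running threshold. Only the imaging comparison is distorted.

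**Irradiation.** No section shows that irradiation lowers QSM. It is an unaddressed competing treatment, nothing more. The Section 8 criterion also covers any CCM lesion and any brain surgery, whereas the scoring problem is sharpest for the index lesion.

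**Size.** The 7/37 were patients whose lesion was excised, a group the trial excludes. The share after a recurrent bleed could be lower or higher. Some expected bleeds may come from other lesions, and any imbalance between arms is assumed.

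**Generic handling exists.** Imputation, the tipping-point analysis and a treatment-rendered analysis of subjects with at least one epoch are planned. But the first two apply only if these scans are declared missing, which the plan never does. Missingness that follows a rebleed fits poorly with missing-at-random given baseline demographics. The no-improvement worst case covers one arm and is milder than +44%.

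These points limit the size and the certainty. The missing rule and the conflict between Sections 9.3.2 and 9.2/9.5 remain.

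**Conclusion.** The concern holds as a gap in the primary analysis rule. The plan retains subjects after index-lesion resection or irradiation but does not say whether their later QSM counts, and the both-periods requirement contradicts the promise to include them.

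Both routes tend to favour the arm with more rebleed-driven surgery. For dropping, this assumes that resected subjects had above-average QSM increases. For scoring, it assumes that QSM falls after resection.

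The effect is probably modest: about 3 to 5 resections, a 9–12% attenuation if they are dropped, and a shift of a few points against the 20-point target if they are scored. All of this rests on an assumed surgery share, assumed rebleed rates by arm, assumed post-resection values, and QSM changes taken from previously stable lesions. It merits correction before unblinding because the affected subjects bear most directly on bleeding and the change costs little.

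**What to change.** 1. Reconcile Section 9.3.2 with Sections 9.2 and 9.5 on who enters the primary intention-to-treat analysis.
2. State that index-lesion QSM is not scored after resection or irradiation of that lesion.
3. Keep every pre-procedure epoch in the linear mixed model instead of requiring both periods.
4. Add interim hemorrhage to the imputation model. Step 6 of the working shows why item 3 alone is not enough. With 20–30% of 40, only about 8 to 12 rebleeders per arm would inform it, so the model must stay simple.
5. Add a missing-not-at-random sensitivity analysis applied to both arms, for example +44% for the affected epoch, labelled as taken from previously stable lesions. A single fixed value understates variance, so it should not be the primary method.
6. Report index-lesion resections and irradiations by arm, with timing relative to the month-12 and month-24 scans.

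Cost: SAP text and some programming, with no extra scans and no change to any clinical rule. The primary analysis set changes slightly, and a few outcomes will rest on model assumptions.

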After satisfying the screening criteria, patients will be assigned a subject number and randomized to the atorvastatin or placebo arm in a 1:1 ratio (See section 3.3 Randomization). This will be implemented upon subject enrollment, and communicated to the Research Pharmacy at the Chicago site via the web-based Electronic Data Capture (EDC) system. Administration of study drug shall continue thereafter, at once daily oral dose for 24 months, with **scheduled visits and repeat imaging at 12 and 24 months from enrollment, and follow-up calls quarterly, and weekly feed back on compliance by electronic monitoring device**. Safety endpoints include a symptomatic intracranial hemorrhage, from the index CA lesion or another source, or a serious adverse event (SAE) necessitating drug discontinuation (Protocol Section 8). If new symptoms arise at any point after starting the study or relevant laboratory test abnormalities, subjects will be contacted by the TN for further assessment and instructions regarding continuation of study intervention, dose de-escalation or discontinuation, based on the study **adverse events management protocol** (See Protocol Section 7). This approach is similar to that used in other statin trials (84, 85, 99, 100, 102, 106, 107, 109).

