#### **9.4.1 Data and Safety Monitoring Team**

The data and safety monitoring team was discussed and approved by the NINDS staff. It will comprise the local IRB, the trial's safety compliance officer (SCO) (Section 10.3.2), and an IMSM from outside the study and data management institutions, assisted by two external medical safety consultants with expertise in CCM disease and in statin therapy respectively. The data and safety monitoring team will provide an ongoing review

of the research, adjudicating adverse events, performing interim safety and efficacy analyses, and assessing progress towards achieving the goals of the study.

Safety assessment will take place at the end of the first year, after 30 participants have completed 12 months of follow-up and again after 60 subjects have completed 12 months of follow-up. Additional reviews will be decided on an ad hoc basis based on the frequency of safety endpoints encountered during the trial. The Brain Injury Outcomes (BIOS) statistician will provide the IMSM and the PI relevant tables including information regarding demographics, rebleeding rates, AEs, SAEs, and radiological and laboratory abnormalities (CT scans, liver function, etc.), per treatment assignments labeled A and B without unblinding. In addition, the IMSM will be provided with a copy of the SAE forms received. Further information will be given to the IMSM upon his/her request. The IMSM will provide written recommendation as to whether the study may continue, possible amendment(s) to the protocol, or whether the study should be stopped. The final decision will rest with the study PI, guided by protocol mandated safety thresholds to suspend and potentially revise or stop the trial (see below). Any protocol revision would require approval by the IRB, and shall be discussed with NINDS staff and external consultants prior to implementation.

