#### **10.4.1.2 Serious Adverse Events (SAEs)**

***Definition of SAEs:*** A serious adverse event is an adverse event that results in any of the outcomes listed below. They generally correspond to Categories B and C adverse events in Table 2.

- Results in death (i.e., the AE actually causes or leads to death). Study investigator agrees to adhere to FDA-defined guidelines and submit an expedited report of any death that is related (even remotely) to study drug.
- Life threatening (i.e., the AE, in the view of the investigator, places the subject at immediate risk of death. It does not include an AE that, had it occurred in a more severe form, might have caused death.).
- Requires inpatient hospitalization or prolongs inpatient hospitalization.
- Persistent or significant disability or incapacity: a substantial disruption of a person's ability to conduct normal life functions.
- Considered a significant medical event by the investigator based on medical judgment (e.g., may jeopardize the subject or may require medical/surgical intervention to prevent one of the outcomes listed above).

**Compulsory SAE:** Certain AEs in the coding guide are defined as potentially serious SAEs if there is a medically qualifying factor. All AEs coded as a grade 4 or 5 will automatically require SAE reporting.

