#### **10.4.4 SAE Reporting**

Any alarming, serious, or unexpected adverse event, including death due to any cause, which occurs during this study, inclusive of the follow up period, and whether or not thought to be related to the test article, must be reported immediately (within 24 hours of learning of the event) to the trial PI, the IMSM and to the local IRB as required. Completion of an SAE form for each SAE that occurs is required to formerly report the event to the trial PI. An expedited safety report will be used by the SCO to notify the PI and IMSM of each serious unexpected suspected adverse reaction, and a running total thereof. This protocol has a pre-specified monitoring plan for determining if subjects receiving the test article are at higher risk for mortality and will only report a death as an expedited safety report if there is evidence of a causal relationship between the test article and the event resulting in death. In addition, an expedited safety report will be used to notify the PI and IMSM if there is an imbalance between the arms suggesting there is a reasonable possibility that the test article caused any of the safety endpoints. Otherwise, the occurrence of these safety endpoints will be reported on an annual basis. The study leadership will submit events meeting the following criteria as expedited Safety Reports according to the guidance and timelines below. The completed case report will be emailed immediately upon completion to the PI and IMSM.

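### Section 8 labels every reason for stopping drug a serious AE and a safety endpoint, and 10.4.1.2 disagrees with Table 2 on what is serious, so the SAE rate and three unnumbered safety triggers depend on which definition is used

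*Combined protocol and SAP*

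**What the plan says.** Section 8 lists eleven bulleted reasons for stopping atorvastatin or placebo and describes them as "designated as serious AEs or Category C in the preceding Table 2". Most are clinical harms. Two bullets are not. One begins "The subject or legal representative withdraws consent, or patient undergoes surgical resection or irradiation of CCM lesion" and goes on to other brain surgery or irradiation. The other reads "Patient develops clinical indications for statin use for cholesterol or cardiovascular indications unrelated to CCM". The rule after the list covers all eleven: "If one or more of these events occur after commencing the study drug, the subject will be considered to have reached a safety endpoint".

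Section 9.1 gives a shorter description and refers to Section 8: "Safety endpoints include a symptomatic intracranial hemorrhage, from the index CA lesion or another source, or a serious adverse event (SAE) necessitating drug discontinuation". Section 6.3.8 separately makes pregnancy a safety endpoint.

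On seriousness, Table 2 heads its three columns mild (A), moderate (B) and serious (C). Section 10.4.1.2 defines SAEs by outcome (death, threat to life, hospitalization, disability, or an event the investigator judges medically significant) but also says of them: "They generally correspond to Categories B and C adverse events in Table 2".

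These terms lead to action in several places:
- 9.4.1: "Additional reviews will be decided on an ad hoc basis based on the frequency of safety endpoints encountered during the trial".
- 10.4.4: an expedited report follows an "imbalance between the arms suggesting there is a reasonable possibility that the test article caused any of the safety endpoints"; otherwise safety endpoints are reported yearly.
- 10.3.2: the independent medical safety monitor (IMSM) may ask which arm is A and which is B if SAEs are unexpected or too frequent.
- 9.2: the SAE rate is a secondary outcome.
- 7.2: serious adverse events listed in Section 8 lead to unblinding of that subject.

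**The concern.** Two terms that the safety plan counts have no single meaning. A safety endpoint is either a clinical harm (the natural reading of 9.1) or any reason for stopping drug (Section 8). A serious event is either Category C (Table 2, Section 8), Categories B and C together (the added sentence in 10.4.1.2), or whatever meets the outcome criteria (the rest of 10.4.1.2).

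The triggers in 9.4.1, 10.3.2 and 10.4.4 carry no number, so what they respond to is set entirely by what is counted. Two people applying the plan in good faith could give the IMSM different tables. They could also reach different conclusions on whether to issue an expedited report, and publish different SAE rates from the same events.

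There is also a consequence for blinding. Section 7.2 ties unblinding to the serious adverse events of Section 8, and Section 8 gives that label to its whole list. Taken literally, a subject who withdraws consent or acquires a cholesterol indication would be unblinded. The two sections have to be reconciled.

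**Working it through.** **1. Denominator.** Section 9.3.1 needs 25 evaluable subjects per arm and expands by 37.5%: 25 / (1 − 0.375) = 40 per arm. This reproduces the plan's figure.

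**2. The Section 8 list against Table 2.**

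| Section 8 item | In Table 2? | An adverse event? |
|---|---|---|
| Hemorrhage, severe allergy, rhabdomyolysis, raised liver enzymes, liver failure, pancreatitis, persistent intolerance | Yes, under C | Yes |
| Pregnancy | No | Safety endpoint in its own right under 6.3.8 |
| Investigator judgment (interaction, glycemic control) | Partly (hyperglycemia) | Depends on the case |
| Consent withdrawal | No | No |
| Surgery or irradiation | No | No (if it follows a bleed, the bleed already counts) |
| New statin indication | No | No |

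The serious/Category C label is therefore wrong for the last three rows, which come from two of the eleven bullets.

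**3. Category B against the seriousness criteria.** Table 2 puts dyspepsia that is intolerable or persists, and nasopharyngitis that is intolerable or recurs, under B. Neither need involve death, threat to life, admission, disability or a significant medical event. The column headed serious has the same fault on a smaller scale: recurrence of either complaint after dose reduction is placed in C.

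**4. Size for the SAE count (illustration).** Section 9.3.2 expects up to 20% of atorvastatin subjects not to tolerate 80 mg: 0.20 × 40 = 8. If all of these are Category B events, the active arm gains up to 8 SAEs under the B-and-C reading. It may gain none under the outcome criteria. The same section expects 20–30% to stop because of symptomatic hemorrhage, which is 8 to 12 of 40. Assuming that these are the only other SAEs and that the groups do not overlap, the count goes from 8 to 16 (2.0-fold) or from 12 to 20 (1.7-fold). Other SAEs would lower the ratio.

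**5. Is hemorrhage monitoring affected?** The threshold in 9.4.2 is more than 40% of the treatment group with symptomatic brain hemorrhage. With 40 treated, 0.40 × 40 = 16, so it takes at least 17. No other Section 8 item enters that count. At full enrolment the binomial probability of 17 or more is 0.11 at the plan's 32.1% natural-history rate and 0.87 at an assumed 50%. Redefining safety endpoints changes neither figure.

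**6. What if someone looked only at the combined count?** Let p be the hemorrhage rate and q the rate of non-harm stops, taken as independent. The combined rate is 1 − (1 − p)(1 − q). Assume p = 30% on placebo and 50% on drug, 40 per arm, two-sided 5% test of two proportions:
- hemorrhage alone: 30% v 50%, power 0.45;
- q = 5% in both arms: 33.5% v 52.5%, power 0.40;
- q = 30% in both arms: 51% v 65%, power 0.24;
- q = 30% on placebo and 5% on drug: 51% v 52.5%.

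An equal rate of non-harm stops dilutes the contrast without hiding it. Only a large opposite imbalance nearly removes it. All values of q and the 50% are assumptions.

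**The case against.** A reader might infer that the combined count can hide an excess of bleeding on atorvastatin. Statins lower LDL, so new cholesterol indications should fall mainly on placebo. With 12 v 9 bleeds and 0 v 3 such stops, the totals read 12 v 12. The documents do not support that inference:
- The only numeric trigger counts hemorrhage alone, and 9.4.2 promises analysis of differential hemorrhage rates throughout.
- Section 9.4.1 sends rebleeding rates to the IMSM by A and B, apart from AEs and SAEs. Section 10.4.1.3 gives bleeds SAE-level review, and 9.5 models them on their own. The 12 v 9 would be seen as 12 v 9.
- The ad hoc trigger is a frequency. Extra events raise it and bring review sooner; they do not cancel bleeds.
- The imbalance report concerns any of the safety endpoints and asks about causation, so it can be read component by component.
- The number of placebo stops has no source. Exclusion 4.2.7 removes subjects with an indication at entry, and only the 12-month lipid profile falls during continuing treatment.

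Two further points have force. Section 9.1 says *include* and refers to Section 8, so it is a looser description and not a strict rival definition. Section 10.4.1.2 gives the B and C correspondence only as a general one, after defining SAEs by outcome. It does not equate them, and a several-fold change in SAE counts does not follow.

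What remains is the mislabelled list, the conflict over seriousness, and the reliance of unnumbered triggers on both. Sections 9.5 and 10.4.2.4 already separate adverse-event stops from other stops, which softens the problem. It also shows that the plan needs the distinction Section 8 erases.

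**Conclusion.** The point holds as an error of definition. Section 8 calls three reasons that are not adverse events both serious AEs and safety endpoints. Section 10.4.1.2 and Table 2 give different boundaries for serious. As a result the SAE rate, the ad hoc reviews, the imbalance report and the request to identify the arms depend on the reading chosen. Sections 7.2 and 8 together, taken literally, extend unblinding to administrative stops.

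The size is modest. On the plan's own ceiling for intolerance, 0 to 8 active-arm events change status, at most about a doubling of the SAE count. That rests on every intolerance being Category B and on hemorrhages being the only other SAEs. It is not a failure of hemorrhage surveillance, which does not depend on these labels.

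**What to change.** 1. In Section 8, move consent withdrawal, surgery or irradiation, and new statin indication to a separate list headed *other reasons for stopping drug*, outside the serious AE/Category C label and outside the safety-endpoint count. The reasons for stopping drug do not change.
2. Keep hemorrhage, adverse events that stop drug, and pregnancy (6.3.8) as safety endpoints, and align 9.1 with that list. Assign stops made on investigator judgment by the determination that 10.4.2.4 already requires.
3. State that everyone who stops drug for any reason is followed to 24 months unless they refuse. Section 8 now attaches that promise to safety endpoints, so moving items out would otherwise leave only 9.3.2 to cover them.
4. Show the IMSM each component by A and B.
5. Delete the B/C sentence in 10.4.1.2, so that seriousness is set only by the criteria listed there. Reconcile the Table 2 column heading and the unblinding sentence in 7.2 with it. Which events lead to unblinding is for the sponsor to settle.

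The cost is an amendment to wording in Sections 7.2, 8, 9.1, 10.4.1.2 and Table 2, with IRB approval, and a few more rows in the safety tables. No new data are needed, since the circumstances of each early stop are already recorded.
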